Two calibrated investigators ([name]) independently performed the color evaluations with the shade guide. The 2 examiners, blinded to the allocation assignment, schedule the volunteers for bleaching and evaluated their teeth against the shade guide at baseline and 1 week after the procedure. The 2 examiners were required to have an agreement of at least 85% (Kappa statistic test) before beginning the study evaluation.

Volunteers with anterior restorations or dental prostheses, with anterior orthodontic apparatuses or with severe internal tooth discoloration (tetracycline stains, fluorosis, pulpless teeth) were not included in the study. In addition, pregnant and lactating women, participants with any other pathology that could cause sensitivity (such as gingival recession, dentinal exposure, visible cracks in teeth), those taking anti-inflammatory or analgesic drugs, those who smoked or volunteers who had undergone tooth-whitening procedures were excluded. Those who reported past or present health problems in the stomach, heart, kidneys or liver; those who reported the continuous use of anti-

inflammatory or analgesic drugs; those patients with diabetes, hypertension or the use of antihypertensive drugs; or patients who reported allergies to dexamethasone and lactose were also excluded from the study.

Sample size calculation: The primary outcome of this study was the absolute risk of TS. The absolute risk of TS (that is, the number of patients [percent] who reported pain at some point during dental bleaching) was reported to be approximately 90% for a similar 35% hydrogen peroxide bleaching product [20,21,36]. Thus, a minimum sample size of 70 participants was required to have a 90% chance of detecting, as significant at the 2-sided 5% level, a decrease in the primary outcome measure from 90% in the control group to 60% in the experimental group.

Random sequence generation and allocation concealment: The authors used blocked randomization (block sizes of 2 and 4) with an equal allocation ration, using a 3rd-party service (Sealed Envelope), which did not intervene in the study. Opaque and sealed envelopes containing the identification of the groups were prepared.

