## Statistical analysis

We performed the analysis after the intention-to-treat protocol, and we involved all participants who were randomly assigned [21]. In cases of missing data, the last observation was carried forward. The statistician was masked to the study groups. The absolute risk of TS and its intensity were evaluated by using Fischer's exact test. ( $\alpha = 0.05$ ). The authors calculated the relative risk as the confidence interval for the effect size.

Comparison of the TS intensity (NRS data) of the 2 groups at the 2 different assessment points were performed by using the Mann-Whitney U test, and comparisons between times within each group were performed using the Friedman test. The comparisons of the TS intensity obtained with the VAS scale were evaluated by using a 2-way repeated measures ANOVA and Tukey's test.

Color changes between groups ( $\Delta$ SGU between base line versus 1 week after the 2nd bleaching session) were compared by using a t test, and the shade changes were evaluated by using Student's t test. In all statistical tests, the significance level was 0.05. We performed all analyses by using the software SPSS for windows version 20.0 (IBM).

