#### Results

We screened 123 participants examined in the dental chair to check if they met the inclusion and exclusion criteria (Figure 1). The bleaching procedures were implemented exactly as planned and no modification was performed.

Characteristics of included participants: The baseline color of the volunteers was similar (control group: 5.9 [1.9]; dexamethasone: 5.6 [2.1]); the mean age (SD) between volunteers was similar between the groups (control: 22.5 [2.1] and dexamethasone: 22.3 [2.7]), ranging from 19 to 29 years. Thirty-four percent of the volunteers from the control group, and 23% of the volunteers from the dexamethasone group were men.

*Protocol adherence and dropouts*: No discontinuity in both treatment groups was found in the clinical investigation. All volunteers attended the recall visit 1 week postbleaching.

*Tooth Sensitivity*: Two volunteers, 1 from each group, took an analgesic to alleviate the bleaching-induced TS (Tylenol, Janssen Cilag Farmacêutica) in the period from 5 to 7 hours after the 2nd and last clinical bleachings.

Table 2 shows the number of participants who experienced TS during the bleaching regimen in the control group and dexamethasone group. In this table, it is shown that no significant difference was observed between groups (p = 0.075). The relative risk, along with the 95% confidence interval, is also evidence that the use of the experimental drug protocol had no effect on the reduction of TS.

Tables 3 and 4 show that the TS was similar in both groups, at different assessment points, in both sessions, using both pain scales. It is also seen that the bleaching-induced TS did not last longer than 48 hours after the bleaching protocol (Tables 3 and 4).

Color Evaluation: Significant whitening was observed in both groups (P < .001). The descriptive data from bleaching obtained after the 1st and 2nd bleaching sessions can be seen in Table 5. At the end of the bleaching protocol, a whitening of approximately 3 shade guide units was detected for both groups.

The results of the subjective shade evaluation (VITA Classical: P = 0.27; VITA Bleachedguide 3D-MASTER: P = 0.68) matched the hypothesis of equality between the groups after bleaching. The effect size and the confidence interval for the overall mean difference is also shown in Table 5 and is evidence of no statistical difference between groups.

Adverse effects: In this study, no reports of adverse effects by volunteers were received.

TABLE 1

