PRODUCT	INGREDIENTS
Pola Office + SDI*	• 37.5% hydrogen peroxide
	
 
potassium nitrate
 

Soothe SDI*	• potassium nitrate 6.0%
	• fluoride ions 0.10%
	• water 89.60%
	• thickener 4.20%
	• sodium benzoate 0.10%
Dexamethasone capsules**	
 
dexamethasone base 8mg
 

•	• starch 50%
	
 
lactose monohydrate 35%
 

	
 
dibasic calcium phosphate 14%
 

	• magnesium stearate 1%
Placebo capsules**	• starch 50%
	
 
lactose monohydrate 35%
 

	
 
dibasic calcium phosphate 14%
 

	• magnesium stearate 1%
Placebo gel**	• carbopol

\* SDI, Victoria, Australia

\*\* Handled by Bem Viver laboratory Ltda, registration number 09047030/0001-28, located at [name]. Batch of the product: 189155.

# TABLE 2

Participants who exp	erienced too	th sensitivity d	uring the bleaching regi	men in the control group	
and dexamethasone g	group*				
TREATMENT	TOOTH SENSITIVITY (N°. OF PARTICIPANTS)		ABSOLUTE RISK	RISK RATIO (95% CONFIDENCE	
	Yes	No		INTERVAL)	
Control	33	2	0.94	0.24 (0.05 1.26)	
Dexamethasone	28	7	0.80	0.24 (0.05 – 1.26)	
* Fischer's exact test	(p=0.075).				

TABLE 3

Medians and interquartile (1 and 3 interquartile) ranges of the tooth sensitivity at different assessment points using the numeric rating scale (NRS).

ACCECCMENT		First Session		Second Session			
ASSESSMENT TIMES	Control	Dexamethason e	Compariso n group	Control	Dexamethason e	Comparison group	
During bleaching	$0(0-1)^{A}$	0 (0-1) A	NS †	0 (0-1) A	0 (0-1) A	NS	
Up to 1h after bleaching	0 (0-1) A	0 (0-1) A	NS	0 (0-1) A	1 (0-1) A	NS	
Up to 24h after bleaching	0 (0-1) A	0 (0-1) A	NS	0 (0-2) A	0 (0-1) A	NS	
Up to 48h after bleaching	0 (0-0) B	0 (0-0) B	NS	0 (0-0) B	0 (0-0) B	NS	

\* Within each column, significant differences are represented by different uppercase letters.

† NS: No significant difference between groups.

TABLE 4

 $Means \ (standard \ deviations) \ of \ the \ tooth \ sensitivity \ intensity \ at \ the \ different \ assessment \ points \ using \ visual \ analog \ scales.*$ 

A COLECCI MENTE	First Session			Second Session		
ASSESSMENT TIMES	Control	Dexamethasone	Compariso n group	Control	Dexamethason e	Comparison group

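### Table 2's risk ratio of 0.24 (0.05 to 1.26) is an odds ratio; the table's own counts give a risk ratio of 0.85 (0.71 to 1.02)

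*Combined protocol and SAP*

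**What the plan says.** The Statistical analysis section names the effect measure: "The authors calculated the relative risk as the confidence interval for the effect size". The sentence is garbled about what is an estimate and what is an interval, but the measure it names is the relative risk.

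Table 2 follows that choice. Its last column is headed "RISK RATIO (95% CONFIDENCE" (the heading continues on the next line), and its single entry is "0.24 (0.05 1.26", that is, 0.24 with limits 0.05 and 1.26. The rows beside it read "Control 33 2 0.94" and "Dexamethasone 28 7 0.80": number with sensitivity, number without, and absolute risk.

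The Tooth Sensitivity paragraph of the Results relies on the entry for its interpretation: "The relative risk, along with the 95% confidence interval, is also evidence" that the drug did not reduce sensitivity. The sample size paragraph of Materials and Methods sets the design target as "a decrease in the primary outcome measure from 90% in the control group to 60% in the experimental group". An odds ratio is mentioned nowhere in the document.

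**The concern.** A risk ratio is one arm's risk divided by the other's. Table 2 prints risks of 0.80 and 0.94 next to a supposed risk ratio of 0.24, and no division of those two numbers gives 0.24. Since the event is very common in both arms, an odds ratio cannot stand in for a risk ratio here.

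This is the only between-group effect estimate reported for the primary outcome, and the Results text cites it. Read as labelled, 0.24 suggests an effect much larger than the one the trial was designed to detect, a risk ratio of 0.60/0.90 = 0.67. The counts show one smaller than that. Anyone who takes the ratio from the table, for instance to pool it with risk ratios from other trials, takes the wrong effect and the wrong interval.

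**Working it through.** **Inputs (Table 2).** Dexamethasone: 28 with sensitivity, 7 without. Control: 33 with, 2 without. Each row sums to 35, which agrees with the 70 volunteers in Materials and Methods and with the Results statement that nobody discontinued. Intervals are two-sided 95%, z = 1.96.

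**Step 1: reproduce the printed figure.** It reproduces as an odds ratio, dexamethasone versus control:

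- OR = (28 × 2)/(7 × 33) = 56/231 = 0.2424
- SE(log OR) = √(1/28 + 1/7 + 1/33 + 1/2) = √0.7089 = 0.842
- 95% CI = exp(−1.417 ± 1.96 × 0.842) = 0.047 to 1.263

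Rounded, this is 0.24 (0.05 to 1.26), a match on all three numbers.

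**Step 2: compute the risk ratio.** Dexamethasone versus control:

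- RR = (28/35)/(33/35) = 28/33 = 0.8485
- SE(log RR) = √(1/28 − 1/35 + 1/33 − 1/35) = √0.00887 = 0.0942
- 95% CI = exp(−0.1643 ± 1.96 × 0.0942) = 0.705 to 1.021

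**Step 3: rule out other sources for 0.24.**

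| Quantity | Estimate (95% CI) |
|---|---|
| Printed entry | 0.24 (0.05 to 1.26) |
| Odds ratio, Woolf interval | 0.24 (0.05 to 1.26) |
| Risk ratio of sensitivity, dexamethasone/control | 0.85 (0.71 to 1.02) |
| Risk ratio of sensitivity, control/dexamethasone | 1.18 (0.98 to 1.42) |
| Risk ratio of no sensitivity, control/dexamethasone | 0.29 (0.06 to 1.28) |
| Risk ratio of no sensitivity, dexamethasone/control | 3.50 (0.78 to 15.69) |
| Odds ratio, conditional exact | 0.25 (0.02 to 1.44) |
| Odds ratio, 0.5 added to each cell | 0.28 (0.06 to 1.29) |

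Only the Woolf odds ratio matches. No risk ratio does, whichever way round it is taken.

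**Step 4: check the label against the table.** A true risk ratio of 0.24 would require a dexamethasone risk of 0.24 × 33/35 = 0.226, about 8 of 35. The table prints 28 of 35.

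**Step 5: size of the discrepancy.** 0.8485/0.2424 = 3.5. The relative reduction is 1 − 0.24 = 76% as labelled and 1 − 0.848 = 15% from the counts. The risk difference, dexamethasone minus control, is 0.800 − 0.943 = −14.3 percentage points.

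**The case against.** The consequences can be argued to be small. The counts and absolute risks stand beside the ratio and are right, so a careful reader sees at once that 0.80/0.94 is not 0.24. Both intervals include 1, the Results draw only a null conclusion, and nobody claims a 76% reduction. The chosen measure, the relative risk, is suitable; the fault is in reporting. All of that is true, and it limits the damage. It does not make the labelled estimate right, and the text leans on that estimate.

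A second objection concerns precision. The odds ratio interval looks much wider, but widths on the two scales are not comparable. The Wald z is −1.417/0.842 = −1.68 for the log odds ratio and −0.1643/0.0942 = −1.74 for the log risk ratio, so the evidence against no effect is almost the same. This stands: the correction does not make the trial more informative. It only stops the wrong interval being read on the risk ratio scale.

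A third concerns the comparison with the design. The planned 90% and 60% correspond to an odds ratio of (0.6/0.4)/(0.9/0.1) = 0.17, so the observed effect falls short of plan on either scale once each is labelled correctly. That also stands. The impression of a larger effect than planned comes wholly from the label, which is the reason to correct it.

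**Conclusion.** The concern holds. The Table 2 entry is the odds ratio with its Woolf interval, presented as a risk ratio. The risk ratio, dexamethasone versus control, is 0.85 (95% CI 0.71 to 1.02), so the printed value is too small by a factor of 3.5 on the scale it claims. The non-significant finding is unaffected, and the counts and absolute risks are correct.

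The conclusion rests only on the Table 2 counts and on denominators of 35 per arm. It is not a claim that the data exclude the planned effect.

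**What to change.** Replace the Table 2 entry with: risk ratio, dexamethasone versus control, 0.85 (95% CI 0.71 to 1.02). State the direction of the comparison, which the table does not give.

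Rewrite the Results sentence to rest on that figure, for example: the risk ratio, dexamethasone versus control, was 0.85 (95% CI 0.71 to 1.02); the interval includes 1, so no significant difference was shown. This is also better than saying the drug had no effect, which an interval from 0.71 to 1.02 does not establish.

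If 0.24 (0.05 to 1.26) is kept, label it an odds ratio and report the risk ratio too. Relabelling alone would leave out the measure that the Statistical analysis section names. The garbled sentence there could be corrected at the same time, to say that the relative risk was calculated with its 95% confidence interval.

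The risk difference of −14.3 percentage points could be added. Its lower limit depends on the method: −29.6 to +1.0 by Wald, −30.7 to +2.0 by Newcombe. It should not be used to argue that the planned 30-point fall is ruled out.

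The cost is one table cell and one or two sentences; no new data are needed. While the row is open, the p-value needs separate attention: 0.075 is the one-sided Fisher value from these counts, and the two-sided value is 0.151. That is a different error, and it also leaves the result non-significant.
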